8.3.1.3 During the Dosing Session

During each Dosing Session:

- The site team will administer the study IMP with 240 mL of water.
- The participant will sit or recline on comfortable furnishings. Participants will be encouraged to bring items to each dosing session which will provide comfort while under the effects of MDMA. This may include comfortable clothes, a personal pillow, soft blanket, music, art supplies, or other supplies to engage in light recreational activities. Eyeshades and a program of music will be provided for the participant if they wish to use them.
- Water will be provided throughout the session at a paced intake, not to exceed three liters overall.

- The site team will collect the following measures at the following timepoints after IMP administration: 30 minutes, 1, 2, 4, 6, 8, 12 hours.
 - Collect PK samples
 - Measure blood pressure, body temperature, and pulse
 - Administer a 12-lead ECG (in triplicate)
 - Measure Subjective Effects VAS
- **Note:** when multiple assessments are scheduled at the same timepoint, the above order of assessments should be observed, so that the PK sample is collected as close to the exact timepoint as possible.
- No food should be allowed for at least 4 hours post-dose. A mid-day meal may be offered at least 4 hours after medication administration, and an evening meal may be offered 4 hours later.
- A member of the site team will remain available to the participant throughout the Dosing Session, see [Section 8.3.3 Psychological Support During Dosing Session](#).

8.3.1.4 End of Dosing Session

Following the final Day 1 Assessments at 12 hours, the site team will complete end of dosing procedures.

- The site team will record AEs and concomitant medications.
- The session may be ended if all medical and psychiatric parameters are acceptable, elevations in vital signs have resolved to pre-IMP levels, the participant is alert, ambulatory, and emotionally stable.

8.3.1.5 Post-Dosing Sessions

Participants will stay in the CRU for at least 36 hours following Dosing Session.

- An optional Integration Session will be offered 24 hours post-IMP to the participant, see [Section 8.3.5 Integration Session](#).
- Following collection of samples and assessments 48 hours post-IMP, participant will be discharged from CRU.
- Participants will return on 72 hours post-IMP for sample collection and assessments.
- The site team will collect the following measures at the following timepoints after IMP administration: 24 hours post-IMP, 48 hours post-IMP, and 72 hours post-IMP.
 - Collect PK samples
 - Measure blood pressure, body temperature, and pulse
 - Administer a 12-lead ECG (in triplicate)
 - Administer Since Last Visit C-SSRS
- Meals are not restricted after the Dosing Sessions.

8.3.1.6 Washout Period and Second Dosing Session

The washout period between Dosing Sessions will be at least 14 days.

- Participants will be reminded not to smoke or use nicotine containing products during the washout period.
- Participants will cross over to the second study arm such that participants initially fasted will be fed and those initially fed will be fasted and repeat the procedures outlined above. The Pre-IMP Meal will only be administered in the “Fed” arm.

8.3.2 Pre-IMP Meal

A high-fat (approximately 50 percent of total caloric content of the meal) and high-calorie (approximately 800 to 1000 calories) meal will be used as a test meal for food-effect evaluation. The targeted macronutrient allocation for the calories of this test meal is as follows: protein (150 calories), carbohydrates (250 calories), and fats (500-600 calories). Following an overnight fast of at least 10 hours, participants will start the recommended meal 30 minutes prior to administration of the drug product. Participants will eat this entire meal in 30 minutes or less.

- An example test meal would be two eggs fried in butter, two strips of bacon, two slices of toast with butter, four ounces of hash brown potatoes and eight ounces of whole milk. Substitutions in this test meal can be made as long as the meal provides a similar number of calories from protein, carbohydrate, and fat and has comparable meal volume and viscosity.

The start and stop time of the start of the high-fat high-calorie pre-dose meal must be recorded. The percent of the total meal consumed by the end of the 30-minute eating period should be recorded. This percentage may be estimated by the study staff.

8.3.3 Psychological Support During Dosing Session

A MAPS-trained study team member will be present during the Dosing Sessions to offer psychological support as necessary. This may be in the form of sitting next to the participant and discussing thoughts or feelings which are emerging for the participant during the session. They will not provide therapy to the participant.

8.3.4 Night Attendant

A night attendant will accompany the participant during the overnight stay. The night attendant's primary function is to ensure the participant is comfortable and has a meal, to provide minimal support, and to alert qualified site staff in case of need expressed by the participant or determined by observation. All night attendants are interviewed, trained, and approved by the site team to ensure they are comfortable providing the necessary support and know whom to call if medical support is needed.

8.3.5 Integration Session

After Day 1 of each Dosing Session, an optional Integration Session will be offered to the participant. The purpose of this session will be to process any thoughts or feelings which emerged as a result of the MDMA and will be facilitated by a MAPS-trained therapist via telemedicine. If necessary, the facilitator will help the participant to reduce any residual psychological distress they are experiencing. The facilitator will be supportive, validate the experience, facilitate understanding and emotional clearing, and offer referral resources for further support as needed.

8.4 Study Termination Follow-up Period and Study Termination

8.4.1 End of Study Visit

An End of Study Visit will take place 2-10 days after day 4 of the second Dosing Session.

After all End of Study Visit procedures are completed, the participant is considered terminated from the study.

8.5 Study Assessments

8.5.1 Primary Outcome Measure

8.5.1.1 PK Blood Sampling

PK samples to determine the bioavailability of MDMA and its metabolites will be collected.

Blood samples will be collected for the determination of plasma concentrations and PK. Additionally, at the occurrence of an SAE, unscheduled blood samples should be collected as soon as possible relative to the event. Blood samples will be collected via a saline flush catheter or by direct venipuncture.

At each timepoint, approximately 2 mL of blood will be collected for the analysis of plasma MDMA and MDA concentrations. Samples will be collected in blood collection tubes containing EDTA K₂ anticoagulant, inverted several times, and immediately placed in an ice bath. The clock times of all blood draws will be recorded and reported for each subject. All tubes will be labeled with a bar code. When scanned, the bar code will provide the SUBJID, protocol ID, anticipated blood draw time point, and actual collection time. Samples should be stored at -20/70° C until it will be transported to the lab for analysis.

The total volume of blood collected for MDMA and MDA PK analysis is approximately 22 mL (11 samples over a period of 72 hours).

Blood samples for determination of plasma concentrations of study drug/metabolite will be analyzed at off-site contract laboratories designated by the sponsor. Samples will be analyzed using a validated bioanalytical method.

When multiple assessments are scheduled at the same timepoint, the following order of assessments should be observed, so that the PK sample is collected as close to the exact timepoint as possible:

1. PK or blood sample
2. Vital Signs

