8.3.1.2 Pre-IMP administration

Prior to each Dosing Session:

- The site team will inquire about any possible changes in health and concomitant medications to ensure the participant continues to meet all eligibility requirements and record AEs, as described in [Section 8.7.5 Method of Detecting AEs and SAEs](#).
- The site team will review procedures for the Dosing Session with the participant and some of the commonly experienced effects of MDMA.
- The site team will administer Since Last Visit C-SSRS.
- Ninety minutes to two hours prior to IMP administration, the site team will collect baseline measures:
 - Collect PK samples
 - Measure blood pressure, body temperature, and pulse
 - Administer a 12-lead ECG (in triplicate)
 - Administer the Subjective Effects VAS
- Thirty minutes prior to IMP administration, for Fed Treatments only:
 - Participants will begin eating a high-fat and high-calorie meal, see [Section 8.3.2 Pre-IMP Meal](#).

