8.6.4 Electrocardiograms

12-lead ECG(s) will be obtained after 5 minutes of rest in a semi-supine position. ECGs will be collected in triplicate using an ECG machine that automatically calculates the heart rate and measures PR, QRS, RR, QT intervals and morphological changes. A 1-minute rhythm strip will also be obtained to screen out participants with arrhythmias at baseline.

12-lead triplicate ECGs will be reviewed by an independent (blinded) reviewer for the purposes of assessing the safety endpoints of mean change from baseline QT interval corrected for heart rate, and any adverse events of special interest that would reflect a serious arrhythmia or suggest a potential for such arrhythmia.

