9.3.3 Safety Analyses

Safety and tolerability will be evaluated. Safety analyses include change from Baseline blood pressure, pulse, and temperature values at specified time points. All laboratory results and vital sign measurements will be summarized using appropriate descriptive statistics.

Adverse event (AE) data will be descriptively evaluated. Descriptive statistics (e.g., number of observations, means, standard deviations, medians, maximum and minimum values) will be used to summarize continuous variables. Frequencies, proportions, and the exact 95% confidence intervals (CI), when appropriate, will be used to summarize categorical variables. Subject listings will also be provided.

Suicidal ideation and behavior will be summarized according to suggestions made in the C-SSRS Scoring and Data Analysis Guide. The number and percent of positive responses of Positive Ideation, Serious Ideation, and Positive Behavior will be tabulated by treatment group and time period (lifetime, screening, baseline, each Dosing Session (pre- and post-IMP), Integrative Sessions, and endpoints). Frequency and incidence of positive or serious ideation and suicidal behavior will be presented using descriptive statistics in tabular format.

ECG analysis: Mean of the triplicate ECGs at each nominal time point will be used for all reporting and analysis; however, individual values will be used to calculate the correction coefficient (γ) for the individual correction QTc (QTcI). Individual correction coefficient, γ , will be estimated using linear regression of log QT on log RR for each subject using all baseline ECG assessments collected before Day 1 dosing within a subject.

The QTc corrections will be individual correction by QTcI = QT/RR^γ , Fridericia's by QTcF = $QT/RR^{0.33}$, and Bazett's by QTcB = $QT/RR^{0.5}$.

Change from baseline ($\Delta QTcI$) will be calculated as the average of the three predose assessments on Day 1 subtracted from the value (i.e., QTc) on Day 1 at a given time t . The effect of MDMA on cardiac repolarization will be assessed, as measured by the time point with the largest upper one-sided 95% confidence limit for the $\Delta QTcI$. The relationship between $\Delta QTcI$ (dependent variable) and MDMA or MDA concentrations (independent variable) will be determined using a linear mixed-effects model.

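### Drawing the PK sample before vital signs and ECG makes every ECG trail its paired concentration; the effect on the concentration-QTc model is modest, and a cheap reordering removes most of it

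*Protocol*

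**What the plan says.** Section 8.5.1.1 of the protocol rules that, at shared timepoints, "the following order of assessments should be observed, so that the PK sample is collected as close to the exact timepoint as possible". The list that follows is PK or blood sample, vital signs, ECG. Section 8.3.1.3 gives the same rule for the Dosing Session, "when multiple assessments are scheduled at the same timepoint, the above order of assessments should be observed", after listing PK sample, blood pressure with temperature and pulse, triplicate ECG, and subjective-effects VAS.

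The post-dose times are "30 minutes, 1, 2, 4, 6, 8, 12 hours" (8.3.1.3), then "24 hours post-IMP, 48 hours post-IMP, and 72 hours post-IMP" (8.3.1.5). The pre-dose set is listed in the same sequence: "Ninety minutes to two hours prior to IMP administration, the site team will collect baseline measures" (8.3.1.2).

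On rest, 8.6.4 states "12-lead ECG(s) will be obtained after 5 minutes of rest in a semi-supine position", and 8.6.3 asks for the same 5 minutes before vital signs. Section 8.5.1.1 allows blood to be taken by flushed catheter or by direct venipuncture, and requires clock times for blood draws. The protocol sets no maximum interval between a sample and its ECG.

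Section 9.3.3 plans a model of the change in QTcI in which the relationship with "MDMA or MDA concentrations (independent variable) will be determined using a linear mixed-effects model". It defines that change from Day 1 values, less the mean of the three pre-dose assessments. Heart rate and blood pressure are also analysed as changes from baseline (section 3.0, Table 2).

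**The concern.** A concentration-QTc model assumes that the concentration and the QTc value describe the same moment. Here the blood is drawn first, and vital signs and a triplicate ECG follow, each requiring rest. The lag always runs the same way. It matters most while concentrations climb quickly. Section 2.2.1 puts onset of effects at about 0.5 to 1 hour and peak effects at 1.25 to 2 hours, so the 0.5 h and 1 h pairs fall in that phase. Those QTc values would be set against concentrations that are too low, and the low end of the fitted line would be distorted.

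A blood draw just before measurements meant to reflect rest may also disturb heart rate and blood pressure.

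The stated purpose of the order is to keep the PK sample on time. That does not require the ECG to come afterwards: the draw can be equally punctual if rest, vital signs and ECG are started early enough before it.

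**Working it through.** **Plan's own figure.** Section 8.5.1.1 states 11 samples and about 22 mL over 72 hours. One pre-dose, seven from 0.5 to 12 h and three from 24 to 72 h give 1 + 7 + 3 = 11, and 11 x 2 mL = 22 mL. This reproduces and confirms the timepoints used below.

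**Inputs.** From the protocol: MDMA half-life 7-9 h (2.2.1) and the sampling times. Assumed: Tmax 1.25-4 h (the lower part, 1.25-2 h, borrows the stated time of peak effect; the upper part allows for slow absorption), absorption lag 0-0.25 h, and a 12-minute sample-to-ECG gap. The protocol gives no such gap. QTc is taken as linear in the concentration at the moment of the ECG, without hysteresis.

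**Model.** C(t) is proportional to exp(-ke(t - lag)) - exp(-ka(t - lag)), with ke = ln 2 / half-life and ka solved from Tmax. The mismatch is C(t + gap)/C(t) - 1.

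**Worked case** (half-life 8 h, Tmax 2 h, no lag, gap 0.2 h). ke = 0.693/8 = 0.0866. ka = 1.518 satisfies ln(1.518/0.0866)/(1.518 - 0.0866) = 2.0. On the usual scale with factor ka/(ka - ke):
- 0.5 h: C(0.5) = 0.519, C(0.7) = 0.632, ratio 1.22, so the concentration at the ECG is 22% above the sample.
- 1 h: C(1.0) = 0.740, C(1.2) = 0.784, ratio 1.06, so 6% above.

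**Range over all assumptions, 12-minute gap.** 12-69% at 0.5 h and 1-19% at 1 h. Later the mismatch is small: at half-life 8 h without absorption lag, gaps of 5-20 minutes give -3% to +6% at 2 h and -3% to 0% at 4 h. The sign turns once the peak has passed.

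**Effect on the planned model.** QTc computed from the concentration at the ECG was regressed on the paired, earlier concentration:

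| Data used | Fitted slope / true slope |
|---|---|
| Day 1 only (pre-dose to 12 h) | 0.93-1.02 |
| All 11 timepoints | 0.98-1.03 |

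The predicted effect at Cmax is off by at most about 3%. The slope moves little because only one or two early pairs are materially displaced. The Day 1 row matters because 9.3.3 defines the QTcI change on Day 1.

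**With the order reversed** (ECG about 3 minutes before the draw, assumed), the 0.5 h mismatch falls to about 4-19% of the sample, now in the opposite direction, and the Day 1 slope error to about 2% or less.

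**Heart rate and blood pressure.** Let the draw add a_pre to the baseline reading and a_post to the post-dose reading. The change from baseline is then wrong by a_post - a_pre. If the two are equal, the error is 0. With an assumed a_pre of 5 units and a_post half as large, it is 2.5 - 5 = -2.5 units. The protocol gives no figure for either.

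**The case against.** The order is a deliberate trade-off. PK is the only primary endpoint, section 3.0 describes the ECG data as supportive, and the listed ECG endpoint (mean change in QTc) needs no concentration pairing. Drawing first keeps the sample punctual even if an ECG has to be repeated. With only 0.5, 1 and 2 h around the expected peak, actual sample times correct AUC for a late draw but cannot recover a missed peak. This stands, and it is why the fix must give the draw priority.

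The gap is also not in the document. Participants already sit or recline during the session, and nothing says that the two rest periods must run one after the other. A shorter gap shrinks every figure above. Pairing rules may also sit in the SAP, which is not shown. That limits the criticism of the analysis, but the order itself is fixed in the protocol.

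Three stronger readings are tempting, and the document does not support them:
- A reader might infer that the hemodynamic endpoints are biased by a needle stick. A catheter is allowed, 5 minutes of rest precede vital signs, and baseline follows the same order, so an equal reaction cancels.
- A reader might infer that the concentration-QTc result is seriously distorted or could hide a signal. The refitted model shows a small error, and at Cmax it is slightly upward.
- A reader might infer a fed/fasted bias from differing absorption speed. Section 2.1 says that the food effect is not well characterised, and 9.3.3 describes no fed-versus-fasted concentration-QTc comparison.

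**Conclusion.** The point holds as a minor, avoidable weakness in a safety analysis. The mandated order makes every ECG later than its paired sample, and the 0.5 h pair, and to a lesser degree the 1 h pair, are materially mismatched. The consequence for the concentration-QTc model is modest: at worst about 7% attenuation of the slope on Day 1 data, which arises with lagged or slow absorption, and about 3% at Cmax. For resting heart rate and blood pressure the preceding draw is a source of noise. Bias would require the reaction, or the draw route, to differ between pre-dose and post-dose, and nothing shows that it does. The primary PK comparison is not touched.

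These sizes rest on the assumed 12-minute gap, the assumed Tmax and lag ranges, a one-compartment profile and no hysteresis. A longer gap or a delayed QTc response could change them, and the protocol cannot settle either.

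**What to change.** In 8.3.1.3 and 8.5.1.1, change the sequence to 5 minutes of rest, vital signs, triplicate ECG, PK draw at the nominal time, then VAS, starting about 10-12 minutes before each nominal time. Use the same order for the pre-dose set in 8.3.1.2, so that baseline and post-dose readings stay comparable. State that the PK draw takes priority at its nominal time if the ECG overruns, and require ECG clock times to be recorded alongside those of the blood draws.

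The cost is wording in these sections and a revised site worksheet, with no added procedures. The downside is that ECG and vital signs fall a few minutes before nominal time, and that a draw may occasionally be late. The priority rule keeps that risk small, and 9.3.2 already calculates PK parameters from actual sample times.

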3. ECG

A detailed document providing standard operating procedures for PK sample collection, processing, storage, and shipment will be provided by the sponsor.

8.5.2 Exploratory Measures

8.5.2.1 Subjective Effects (SE)

The subjective effects (SE) chosen are based on literature reviews of subjective effects of MDMA among healthy volunteers in controlled studies [27, 28]. Subjective effects will be collected using the visual analog scale (VAS) on 14 items: negative mood, body perception changes, confusion, difficulty concentrating, compassion for self, compassion for others, positive mood, intellectual efficiency, social, calmness, talkative, open to new experiences, meaningful experience, emotional distress. VAS items are rated on a series of 100 mm long lines, marked from 'not at all'

on the left to ‘extremely’ on the right. The SE measure takes approximately 10 minutes to complete.

8.6 Safety Assessments

Additional visits or repeat assessments (in person, at home, by telephone, or via tele-assessment) may be scheduled at the discretion of the study staff to collect more information for determining eligibility or to discuss study expectations with the potential participant.

8.6.1 Suicidal Ideation and Behavior Risk Monitoring

Participants will be monitored appropriately and observed closely for increases in suicidal ideation and behavior (SIB) or any other unusual changes in behavior. Participants who experience increases in SIB should undergo a risk assessment.

Baseline assessment of suicidal ideation and behavior/intervention-emergent suicidal ideation and behavior will be monitored during the study using the MAPS Adapted C-SSRS.

8.6.1.1 MAPS Adapted Columbia-Suicide Severity Rating Scale (C-SSRS)

The C-SSRS is a clinician-administered measure of suicidal behavior devised to detect potential suicidal thoughts or behaviors during a clinical study [29]. It consists of a Baseline/Screening version and a Since Last Visit version that assess suicidal ideation, ideation intensity, and behavior. The C-SSRS consists of a series of questions and can be administered during a face-to-face interview or over the telephone. The Baseline/Screening version will only be administered at the initial Screening visit. All subsequent administrations will utilize the Since Last Visit version. Participants who are discontinuing medications to participate in the study will complete the C-SSRS before and after medication washout. The C-SSRS Intensity scale obtained a Cronbach’s alpha of 0.94 for the Since Last Visit form, and Last Visit MAPS-adapted C-SSRS severity scores were positively correlated with the BDI “suicide thoughts” item [30]. The MAPS Adapted C-SSRS was developed utilizing [name] Columbia Suicide Severity Scale. The MAPS Adapted C-SSRS maintains the content and flow of the standard C-SSRS. The scale was adapted to modify formatting and add additional administrative guidance to reduce rater and data entry errors. The MAPS Adapted C-SSRS has been approved by [name] for use in MAPS Research and is referred to throughout the protocol as C-SSRS. The MAPS Adapted C-SSRS takes approximately 10 minutes to complete.

8.6.2 Physical Examinations

A complete physical examination will include, at a minimum, assessments of the cardiovascular, respiratory, gastrointestinal, integumentary, and neurological systems. Traumatic Brain Injury (TBI) assessment with residual neurological signs or symptoms should be included as part of this exam. Height and weight will also be measured and recorded, which will be used to calculate Body Mass Index (BMI). A brief physical examination will include, at a minimum, assessments of the skin, lungs, cardiovascular system, and abdomen (liver and spleen). Investigators should pay special attention to clinical signs related to previous serious illnesses.

